Cover Page for ClinicalTrials.govs

Official Title of the Study:

Acceptance and Mindfulness Based Exposure Therapy For Survivors Of Sudden Cardiac Arrest

NCT Number:

NCT04596891

Principal Investigator:

[name]

[contact]

[contact]

Date of Document:

09/30/2022

Statistical Analysis Plan

Study analyses will employ SPSS Statistics version 28.0. This feasibility study was not powered to detect treatment effects. Separate repeated measures ANOVAs will be conducted for CAPS-5 and HAM-D scores over time will explore treatment effects on psychiatric symptoms. For completers, paired sample *t*-tests will compare symptoms at baseline, posttreatment, and 3-month follow-up using all available data. Cohen's *d* will be computed to determine effect sizes. Descriptive statistics will describe the proportion of patients achieving PTSD remission (defined *a priori* as no longer meeting PTSD diagnostic criteria and CAPS-5 score ≤ 23) or clinically significant response ($\geq 30\%$ reduction from pretreatment CAPS-5). To classify HamD-17 depression severity, we will follow recommendations of Zimmerman et al.: not depressed (0–7), mild (8–16), moderate (17–23), and severe depression (≥ 24).

The first recorded 7200 minutes of Fitbit actigraphy use (confirmed by pulse recording) post account activation will define the baseline and will be compared to final treatment week in separate paired samples *t*-tests for average daily steps, sedentary minutes, and minutes asleep. Analyses will exclude patients lacking 7200 minutes of final week active wear.

Protocol Title:
**ACCEPTANCE AND MINDFULNESS BASED
EXPOSURE THERAPY FOR SURVIVORS OF
SUDDEN CARDIAC ARREST**

Version Date:
09/30/2022

Protocol Number:
8017

Research Area:
Anxiety, Mood, Eating & Related Disorders
Division:
Anxiety/PTSD/OCD

Expiration Date:
07/19/2023

Co-Investigator(s):
[name]
[name]
[name]

Contact Principal Investigator:
[name], PHD
Email: [contact]
[contact]

Research Chief:
[name]

Department & Unaffiliated Personnel

Department

What Department does the PI belong to?
Anxiety Disorders Clinic
Within the department, what Center or group are you affiliated with, if any?
PTSD Team

Unaffiliated Personnel

List investigators, if any, who will be participating in this protocol but are not affiliated with New York State Psychiatric Institute or Columbia University. Provide: Full Name, Degrees and Affiliation.
PTSD Team

Amendment

Describe the change(s) being made

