[name], Columbia University

[name], Columbia University

[name], Columbia University

[name], Columbia University

[name], Columbia University

[name], Columbia University

[name], Columbia University

[name], Columbia University

Application for Continuation of Research

Status

Current Status of Study:

All research interventions were completed. Only data analysis is ongoing.

Summary of Experiences to Date

Please provide a summary of scientific progress of the study and the experience of research participants, to date. This requirement is designed to allow for the investigator and the IRB to reassess the study's risks and benefits in terms of developments in the field, changing practice patterns, and new IRB policies and procedures.

To date we have enrolled 11 participants (7 female and 4 male). Ten participants completed the intervention, while 1 participant decided to discontinue study involvement. No serious adverse events have occurred, and all interventions have been well tolerated. There have not been any study findings, recent literature, or untoward events in the past year which might affect the analysis of the safety, risks, or benefits of study participation.

Funding

Have there been any changes in funding status since the prior approval?

No

Have the principal investigator and other investigators made all required disclosures of financial interest in the study sponsor/product?

Yes

Summary

Have there been any study findings, recent literature, or untoward events occurring here or at other sites in the past year which might affect the analysis of the safety, risks or benefits of study participation?

No

Have there been any serious adverse events (serious and/or unanticipated problems involving risks to subjects or others at this site which occurred in the past year)?

No

Have all study staff with a significant role in the design or implementation of the human subject components of this study received required training in human research subject protections?

Yes

Is the study covered by a certificate of confidentiality?

No

Overall Progress

Approved sample size

14

Total number of participants enrolled to date

11

Number of participants who have completed the study to date

10

Have there been any significant deviations from the anticipated study recruitment, retention or completion estimates?

No

Comments / additional information

Sample Demographics

Specify population

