This pilot trial seeks to examine feasibility, acceptability, safety, and preliminary efficacy of a new behavioral treatment for survivors of sudden cardiac arrest with clinically elevated symptoms of post traumatic stress disorder (PTSD). While several well-studied, validated treatments for PTSD exist, to date, there is no evidence-based treatment for PTSD in cardiac arrest survivors. Standard PTSD interventions targeting fear extinction and threat perception in the context of current safety pose a problem in a population that is living with an actual ongoing cardiac threat. Thus, we will be developing a *de novo* protocol for an Acceptance and Mindfulness-Based Exposure Therapy (AMBET) intervention that targets increased discriminatory perception through mindful interoceptive attention and adaptive threat responding. To assess

whether patients' medication adherence and physical activity are improved over the course of treatment, participants will be provided with a wearable device (Fitbit wristband) to monitor their physical activity.

The specific aims of this study are to: (1) develop an acceptable protocol for an AMBET intervention for survivors of sudden cardiac arrest with elevated PTSD symptoms (2) examine its safety and feasibility in a small sample of 14 patients (3) investigate acceptability and feasibility of the measurements including a physical activity monitoring device.

The subject population will consist of cardiac arrest survivors with clinically diagnosed PTSD (n=14; CAPS-5 \geq 23). In Phase 1 (interview phase), with the aim to develop a treatment manual, 14 SCA survivors will be interviewed about their symptoms and evaluated for baseline assessment. In Phase 2 (treatment phase) the same participants will be treated with eight sessions of AMBET. Participants will be evaluated at baseline, at treatment mid-point (week 4), and at the end of treatment.

Background, Significance and Rationale

Background, Significance and Rationale

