The goals of the AMBET treatment will be to reduce PTSD symptoms and hypervigilance to internal stimuli (i.e., interoceptive bias), and increase cardiovascular health behaviors (medication adherence, physical activity) following cardiac arrest. Following psychoeducation about PTSD and cardiovascular disease (CVD) related health behaviors, participants will be engaged in in vivo and imaginal exposure exercises to reduce avoidance responses. Participants will be introduced to acceptance and mindfulness-based strategies that will be practiced in session and as homework assignments. Sessions will be delivered to patients individually through HIPAA-compliant zoom-hosted video visits. A meta-analysis of remote (e.g., telepsychiatry; video-based) treatments for PTSD found these treatments superior to waitlist conditions. Compared to face-to-face treatments, videoconferencing CBT treatments did not result in significantly different PTSD outcomes at post-treatment(30).

Specific Aims and Hypotheses

Specific Aims and Hypotheses

The specific aims of this study are to: (1) develop an acceptable protocol for an AMBET intervention for survivors of sudden cardiac arrest with PTSD; (2) examine its safety and feasibility in a small sample of 14 patients; (3) investigate acceptability and feasibility of the measurements including a physical activity monitoring device.

Hypothesis 1: The AMBET intervention will demonstrate preliminary tolerability (<20% dropout)

Hypothesis 2: The AMBET intervention will demonstrate efficacy (pre/post decrements on psychological distress) and the recruitment goal (n=14) will be met.

Hypothesis 3: Participants will find the health behavior monitoring technology acceptable and comply with study procedures (wearing Fitbit device daily and during sleep.)

Description of Subject Population

Sample #1

Specify subject population

Survivors of sudden cardiac arrest with clinically diagnosed PTSD (CAPS-5 =23)

Number of completers required to accomplish study aims

10

Projected number of subjects who will be enrolled to obtain required number of completers

14

Age range of subject population

18-85

Gender, Racial and Ethnic Breakdown

Gender:

50% female (N:5-7)

50% male (N:5-7)

Ethnicity:

25% Hispanic

45% White

30% African-American

Description of subject population

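### The SAP plans uncorrected Cohen's d on at most 10 completers, with no interval and no named standardiser; Hedges' g with a 95% CI would be a cheap improvement

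*Combined protocol and SAP*

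**What the plan says.** The effect-size plan is one sentence in the Statistical Analysis Plan: Cohen's d "will be computed to determine effect sizes". It follows the sentence on completers, whose paired "tests will compare symptoms at baseline, posttreatment, and 3-month follow-up using all available data". I therefore read d as belonging to those within-person comparisons of CAPS-5 and HAM-D. The SAP does not say which SD divides the change, whether a small-sample correction applies, or whether an interval will be given.

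The number of pairs is small by design and now fixed. Under Description of Subject Population, the entry for "Number of completers required to accomplish study aims" is 10. The Summary of Experiences to Date reports: "Ten participants completed the intervention, while 1 participant decided to discontinue study involvement". The Status entry says that interventions are finished and only analysis continues.

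On the role of the estimate, the SAP states: "This feasibility study was not powered to detect treatment effects". The Lay Summary nevertheless includes efficacy among the purposes: "This pilot trial seeks to examine feasibility, acceptability, safety, and preliminary efficacy of a new behavioral treatment". Hypothesis 2 goes further: "The AMBET intervention will demonstrate efficacy (pre/post decrements on psychological distress", with no target effect size.

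**The concern.** Because the study claims no power, its p-values carry little weight. The size of the pre-post change and its precision are what a reader will take from the efficacy analysis, alongside the planned remission and response proportions. Three things weaken d as that summary.

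- With few pairs, uncorrected d is biased upward, because the SD in the denominator is poorly estimated.
- Without an interval, a single value such as 0.8 gives no sign of how little 10 pairs can say.
- Without a named standardiser, the same data can yield noticeably different values of d, and readers cannot tell which they have been given.

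What is at stake is how strong the preliminary efficacy signal appears. No test, response rate or feasibility conclusion depends on it.

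**Working it through.** The documents give no effect size, SD or correlation, so there is no stated figure to reproduce. Values of d and of the pre-post correlation r below are illustrative assumptions.

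**Inputs from the documents.** Paired comparisons in completers (SAP); 10 completers of 11 enrolled (Summary of Experiences to Date). With all 10 pairs, df = 10 − 1 = 9. The documents do not give the number of pairs at each visit, so 7 to 9 pairs are also shown.

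**1. Average bias.** For a standardiser with m df, Hedges' factor is J(m) = Γ(m/2) / [√(m/2) · Γ((m−1)/2)], and the expected value of d is the true value divided by J. At m = 9, J = Γ(4.5) / (√4.5 · Γ(4)) = 0.914. The usual approximation, 1 − 3/(4·9 − 1), agrees at 0.914. Then 1/J = 1.094, so d is 9.4% too large on average.

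| Pairs | df | J | Average overstatement |
|---|---|---|---|
| 10 | 9 | 0.914 | 9.4% |
| 9 | 8 | 0.903 | 10.8% |
| 8 | 7 | 0.888 | 12.6% |
| 7 | 6 | 0.869 | 15.1% |

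These rows apply to the SD of change or the baseline SD. If the two SDs are averaged, the approximate df at n = 10 is 2·9/(1 + r²). That gives 18 at r = 0 (4.4% overstatement), 14.4 at r = 0.5 (5.6%) and 9.94 at r = 0.9 (8.4%).

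**2. Sampling error.** For d on the SD of change, d·√n follows a noncentral t with n − 1 df. Inverting it at n = 10 gives these 95% intervals:

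- observed d = 0.5: −0.17 to 1.15
- observed d = 0.8: 0.07 to 1.50
- observed d = 1.0: 0.21 to 1.75

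At a true value of 0.8, the mean of d is 0.8/0.914 = 0.875, a bias of 0.075. The SD of d is 0.43. The bias is therefore 0.075/0.43 = 0.17 of the sampling SD.

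**3. How often d is too high.** From the same distribution at n = 10, for true values of 0.5, 0.8, 1.0 and 1.5, uncorrected d exceeds the truth in 52%, 53%, 53% and 54% of samples.

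**4. Choice of standardiser.** With equal SDs at the two visits, d on the SD of change divided by d on the raw SD equals 1/√(2(1 − r)). This is 0.85 at r = 0.3, 1.00 at r = 0.5, 1.29 at r = 0.7 and 1.58 at r = 0.8.

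**5. Effect of the correction.** An observed d of 0.8 with 9 df becomes g = 0.914 × 0.8 = 0.73. The proportional reduction is 1 − 0.914 = 8.6%.

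**The case against.** The strongest reply is that this is an openly exploratory pilot. Its specific aims are protocol development, safety and feasibility, and acceptability of the measurements. Remission and response proportions are planned too, so d is not the only efficacy output. The bias is under a fifth of the sampling SD at a true value of 0.8, and using g instead of d alters no test or feasibility conclusion. All of this stands, and it is why the point is low in severity. It does not defend the missing interval: the more sampling error dominates, the more the interval is needed.

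It is also fair to say that the 9% is conditional. It holds for a 9-df standardiser and falls to about 4% to 8% if two SDs are averaged. Likewise, the standardiser changes d by more than half only at the highest correlation assumed here (0.8); at 0.5 it makes no difference.

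A reader might infer that any later trial planned from this d would be too small. The documents do not support that, for three reasons.

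- The bias is an average. In 46% to 48% of samples, for true values of 0.5 to 1.5, uncorrected d falls below the truth.
- Nothing in the protocol or SAP says that d will be used to size a trial. The Background section states a long-term goal of determining effectiveness, which is not the same thing.
- A single-arm pre-post d in completers is not a between-arm effect. It includes natural recovery and regression to the mean, and its size depends on r when the SD of change is the divisor. Putting it into a two-arm sample-size formula, corrected or not, would be unsound.

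**Conclusion.** The point holds as a cheap, low-severity improvement to a stated method. The SAP plans uncorrected Cohen's d on at most 10 pairs, with no stated interval or standardiser. On average d will be about 9% too large with a 9-df standardiser, about 4% to 8% too large if two SDs are averaged at 10 pairs, and 11% to 15% too large with 9 to 7 pairs on a single-SD standardiser. The absent interval matters more than the bias: at n = 10 an observed d of 0.8 is compatible with anything from 0.07 to 1.50.

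These figures assume normally distributed changes (and scores, for the raw-SD versions). The intervals apply to d on the SD of change. The standardiser ratios also assume equal SDs and the correlations shown. No conclusion follows about the size of any later trial.

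**What to change.** Replace the Cohen's d sentence in the SAP with one that does the following for each CAPS-5 and HAM-D comparison:

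- report Hedges' g (d multiplied by the small-sample factor for the df of the chosen standardiser) with a 95% CI;
- name the standardiser beside each value;
- give the raw mean change in scale points with its 95% CI and the number of pairs.

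This needs no new data, and analysis is still under way according to the continuation report. The cost is a sentence or two of text. The downside is presentational: effect sizes become up to about 9% smaller at 10 pairs, and their imprecision becomes visible.

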The protocol will be carried out remotely. Video-visits and assessments will be conducted over HIPAA-compliant Zoom (utilizing licensed NYSPI accounts), a password protected and HIPAA compliant electronic platform. For consent forms and self-report measures, NYSPI REDCap will be utilized to gather signatures and information from patients. Patients will receive an email with a weblink to complete these on this HIPAA compliant platform and the data will be stored on secure NYSPI servers.

Approximately 7-10 days after completion of intake interview, participants will receive a package from the study team that will include the Fitbit required for study participation, along with instructions for how to use this device. Participants will be provided with a commercially available Fitbit Inspire HR, equipped with a highly sensitive accelerometer to track activity as well as sleep quantity and sleep quality characteristics (This product has previously been approved by the CUIMC IRB and used successfully in studies conducted by Center for Behavioral Cardiovascular Health). The Fitbit will be registered with a study ID and password and participants will be instructed to download the Fitbit app to their phone to sync. Participants will be asked to continuously wear the Fitbit throughout the study period, including regularly charging the Fitbit once per week and wearing the device during sleep. The participant will receive push notifications to recharge the Fitbit if its battery is running low or if the Fitbit disconnects for a prolonged period of time (>24 hours).

Flow Chart of Study Procedures:

Visit 0: Eligibility Assessment (Review of medical records and phone screening). Potential patients will be asked by [name] team to contact the study research assistant who will schedule a phone screen with the patient. Alternatively, participants who respond to the flyer may also self-refer to the study by contacting the research assistant listed on the advertisement. If patient is potentially eligible after completing the phone screen, a clinical evaluation will be conducted by the PTSD program clinicians.

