A manual will be developed to provide clear structure for the course of treatment and will be forwarded to the IRB when a more complete draft has been finalized. All study therapists conducting the AMBET sessions will be trained clinicians at master's or PhD level who have completed training in the protocol and who have experience delivering exposure therapy to treat traumatic stress. Study therapists will be supervised by a licensed psychiatrist. The clinician will first provide psychoeducation regarding PTSD symptoms that can ensue after medical trauma and then introduce the rationale for the treatment. The principal treatment content can be summarized as: explore personal values and impact of avoidance behaviors on well-being, increase functional interoceptive awareness and cardiovascular symptom discrimination through mindfulness and defusion exercises, approach feared events and activities through values-based exposure, and create meaning and cohesion through flexible perspective taking. The protocol will primarily target:

1. Maladaptive behavioral responses related to fear (particularly avoidance)
2. Hypervigilant interoceptive attention and catastrophic bias
3. Engagement in heart-healthy behaviors such as physical activity and medical adherence.

The specific interventions are:

- A) Mindfulness exercises to increase functional interoceptive awareness and discrimination of benign/malign symptoms for more accurate threat perception and adaptive responding.
- B) Exposure exercises to physical sensations that are similar to cardiac symptoms (e.g., palpitations due to

physical activity or anxious arousal) to reduce symptom-related hypervigilance and increase adaptive threat responding. Values exploration to increase motivation for engagement in in-vivo, imaginal, and interoceptive exposure exercises.

C) Increased physical activity to reduce depressive symptoms and improve cardiovascular health.

Therapist adherence to protocol: All sessions will be videotaped and reviewed for adherence to the treatment protocol.

You can upload charts or diagrams if any

Criteria for Early Discontinuation

Criteria for Early Discontinuation

Principal Investigator and/or Co-Principal Investigators, will review (at minimum) all currently enrolled patients in a weekly meeting.

1. Requests to withdraw from the study.

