Client Satisfaction Questionnaire (CSQ-3) (2 minutes)
TEQ (2 minutes)
Life Events Checklist (LEC) (5 minutes)
CSQ-3 (5 minutes)
MAIA (5 minutes)

CAQ (5 minutes)
HADS (5 minutes)
SCID (30 minutes)
MMSE (20 minutes)
MMAS-8 (5-minutes)
ASI-3 (2 minutes)

Please attach copies, unless standard instruments are used

Research Related Delay to Treatment

Will research procedures result in a delay to treatment?

Yes

Maximum duration of delay to any treatment

All effort will be made to arrange an intake as soon as possible, within a few days of initial contact if possible. Clinical staff will meet weekly to discuss new intakes, and disposition to active treatment will be made as soon as patients have been found eligible and have signed informed written consent. We expect that patients should enter treatment within two weeks of initial intake date. This allows time to review the qualitative information from the initial intake interview to develop individualized treatment plans within the scope of the treatment protocol as well as for delivery of Fitbit device and HIPAA-compliant zoom video call training. The patient will have immediate access to the intake clinician and study-team psychiatrist if he or she presents with an emergent clinical issue.

Maximum duration of delay to standard care or treatment of known efficacy

The maximum delay before active treatment of known efficacy is offered will be 12 weeks from baseline assessment. However, we are not excluding survivors who are currently in other treatment (provided there has been no change in treatment in previous three months) so for these there will be no delay in treatment.

Treatment to be provided at the end of the study

Participants will be referred for further treatment as needed. The types of referrals offered may include general referrals to other treatment clinics and centers in the tri-state area, or more specifically referrals may be offered as preferred to trauma-focused therapists, low-cost therapists and clinics, or to veteran specific services.

Clinical Treatment Alternatives

Clinical treatment alternatives

Patients who do not participate in research will be referred to treatments for PTSD in the community, such as cognitive behavioral therapy, prolonged exposure therapy, interpersonal psychotherapy for PTSD, or psychopharmacology depending on the clinical evaluation and their expressed preferences.

Risks/Discomforts/Inconveniences

Risks that could be encountered during the study period

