Psychological Distress: Exposure treatments pose some risk of psychological discomfort. Participants may find that discussing trauma related memories or facing feared situations may increase emotional distress. The treatment protocol will start with introduction to grounding techniques such as diaphragmatic breathing and mindfulness-based techniques for distress management and emotion regulation, and participants will practice these in session with clinician. Patients will also be informed that they can contact their clinician between sessions for support and to troubleshoot homework exercises. The treatment will be delivered by a clinician with experience in treating PTSD with exposure therapy. Additionally, as with any time-limited treatment, patients may feel uncomfortable when treatment ends. This is an issue that patients will be encouraged to discuss with their therapist, and treatment will be provided by a clinician experienced in delivering short-term treatments.

Loss of Confidentiality: A potential risk from this study is the violation of the participant's privacy, since patient medical information will be used as a source of data. Special protections against this risk are provided (see below).

Identification of Severe Mental Illness: There is the possibility that we will discover during screening that participants have significant cognitive or alcohol/drug impairments that disqualify them from participating in the study. It may be discovered during screening or during assessment that a participant has severe depression that warrants immediate treatment. Should the subject express suicidal ideation at any time during the assessment or treatment, the study clinician will be contacted immediately to assess the subject and to determine the appropriate course of action.

During intake, treatment and assessment, participants will be required to confirm the address where they are located at the start of each remote session as well as to provide the study team with the telephone number to an emergency contact. Participants will be required to provide a response to suicidality item on BDI-II prior to each session. If a patient would endorse suicidal thoughts, clinician or assessor would further assess risk.

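### The Fitbit baseline has no cut-off at session 1, so on the protocol's approximate timings it could include treatment days for some patients

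*Combined protocol and SAP*

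**What the plan says.** The Statistical Analysis Plan defines the Fitbit baseline by accumulated wear: "The first recorded 7200 minutes of Fitbit actigraphy use (confirmed by pulse recording) post account activation will define the baseline". That window is compared with the last week of treatment in three paired t-tests, one each for steps, sedentary time and sleep time. The only wear condition applies to the later window: "Analyses will exclude patients lacking 7200 minutes of final week active wear".

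The timing comes from the protocol. Study Procedures says of the device: "Approximately 7-10 days after completion of intake interview, participants will receive a package from the study team". Meeting 1 contains both the baseline assessment and the intake interview, so one day can serve as day 0. Research Related Delay to Treatment says: "We expect that patients should enter treatment within two weeks of initial intake date". It explains the interval as time for reviewing the interview and planning treatment, "as well as for delivery of Fitbit device and HIPAA-compliant zoom video call training". Delivery is mentioned there, but days of wear before treatment are not.

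No section of the combined document ends the baseline at session 1, sets a deadline for activating the account, or makes session 1 depend on the window being full.

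**The concern.** The Lay Summary gives change in physical activity over treatment as a reason for supplying the device, and Study Procedures lists increased activity among the specific interventions. The three t-tests are the SAP's only analysis of the Fitbit data. They read naturally as a comparison of patients before and at the end of treatment.

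That reading needs a baseline that stops before treatment starts. A window that closes only when a wear total is reached can run past session 1 if the device arrives late or is worn for only part of the day. If activity had begun to change by then, the later days would probably dilute the measured difference. As the SAP stands, the analysis would not show whether this had happened.

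**Working it through.** The plan gives no figure to reproduce here, so the check is timeline arithmetic.

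**Inputs**
- Window length: 7200 worn minutes (Statistical Analysis Plan).
- Receipt day R: 7, 8, 9 or 10 after intake (Study Procedures).
- Session 1 day S: 14, the end of the expected two weeks (Research Related Delay to Treatment).
- Assumptions: the account is activated on the day of receipt, and both timings count from the same intake day.

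**Step 1. Days needed to fill the window, D**
- Continuous wear: 7200 / 1440 = 5.0 days.
- Lowest average wear that passes the final-week rule: 7200 / (7 × 60) = 17.1 h/day, which gives D = 7.0 days. The SAP sets no wear rate for the baseline, so this rate is borrowed from the other window as a reference point.

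**Step 2. Share of the baseline falling after session 1** = max(0, D − (S − R)) / D, with S = 14

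| Receipt day R | Days before session 1 (14 − R) | Share, continuous wear (D = 5) | Share, 17.1 h/day (D = 7) |
|---|---|---|---|
| 7 | 7 | 0 | 0 |
| 8 | 6 | 0 | 1/7 = 14% |
| 9 | 5 | 0 | 2/7 = 29% |
| 10 | 4 | 1/5 = 20% | 3/7 = 43% |

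The wear needed to finish by day 14 is 120 h / (14 − R): 17.1, 20, 24 and 30 h/day for receipt on days 7, 8, 9 and 10. The last is impossible, so a day-10 receipt with a day-14 start overruns at any wear level.

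**Step 3. When the overlap disappears.** The earliest session 1 with no overrun is R + D. This is day 12, 13, 14 or 15 at continuous wear, and day 14, 15, 16 or 17 at 17.1 h/day. A session 1 on day 17 or later is therefore clean for every receipt day at either wear level.

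**Step 4. What a cut-off at session 1 would leave.** With S = 14, the most that can be recorded beforehand is (14 − R) × 1440: 10,080, 8,640, 7,200 or 5,760 minutes. A restricted baseline cannot always reach 7200 minutes, so it needs its own minimum-wear rule.

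**The case against.** The strongest reply is that both timings are soft. One is approximate and the other is an expectation, not a limit. The same section sets a ceiling of 12 weeks from baseline assessment before treatment of known efficacy is offered. Eight weekly sessions span about 7 weeks from first to last, so the protocol tolerates a session 1 well after day 14. Participants are asked to wear the device continuously, and four of the eight cells in the table are zero. The mailed Fitbit instructions are not in the document and might address early wear.

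The consequence is also limited. The overlap in the table is at most 3 days, and because sessions are weekly, those days follow a single session. Of the opening content, Study Procedures says: "The clinician will first provide psychoeducation regarding PTSD symptoms". Risks/Discomforts/Inconveniences adds: "The treatment protocol will start with introduction to grounding techniques such as diaphragmatic breathing". Physical activity enters the plan only with the treating physician's agreement. The SAP states: "This feasibility study was not powered to detect treatment effects". No hypothesis rests on these t-tests: Hypothesis 2 concerns psychological distress and recruitment, and Hypothesis 3 concerns acceptability and wear.

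All of this stands, and it limits the weight of the point. It does not supply the missing cut-off. Late activation, lower wear or an earlier session 1 would enlarge the overlap just as a later session 1 would remove it.

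Three stronger readings are tempting, and the documents do not support them:
- **That the baseline was contaminated.** No activation, wear or session dates are given.
- **That the activity change is understated by up to 43%.** That figure is a share of the window. How far activity moved in the days after session 1 is unknown, so neither the size nor the direction of any bias can be computed.
- **That a baseline cut at session 1 should replace the written one.** Interventions are complete, and the cut window would have no minimum wear while the final week still requires 7200 minutes. Making it the main analysis now would add discretion in a very small sample.

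**Conclusion.** The definition permits treatment days in the baseline, and the protocol's own timings make this plausible for some patients. With session 1 on day 14 and activation on receipt, the share after session 1 is 0 to 20% at continuous wear and 0 to 43% at 17.1 h/day. It is zero at both wear levels if session 1 falls on day 17 or later. These ranges depend on the approximate timings and the assumed wear. They are not estimates of what occurred, and the number of patients affected cannot be found from the documents.

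The point concerns the interpretation of three exploratory t-tests in at most 10 completers, the number given in the Application for Continuation of Research. It does not affect the CAPS-5 or HAM-D analyses or any stated hypothesis. It is worth acting on because the sponsor can settle it from data already held.

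**What to change.** 1. Keep the written 7200-minute baseline as the main Fitbit analysis.
2. Report how many baseline windows crossed session 1, and each patient's worn minutes before session 1.
3. Add a comparison that uses only baseline minutes recorded before session 1, averaged per day of wear. Fix its minimum-wear rule before change scores are viewed, or label the analysis post hoc if they have already been seen.
4. Describe the result as a change from before treatment to the end of treatment only if no window crossed session 1 or the two versions agree. With so few patients, judge agreement on the direction and size of the mean change, not on significance.

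The cost is a few lines of SAP text and a re-cut of existing data, since the Application for Continuation of Research says that only analysis remains. The drawback is that some patients will have a shorter, noisier baseline, or none, in the added comparison. If no window crossed session 1, the count in item 2 closes the matter.
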